3.1.2 Rational for the use of MRI Perfusion

MRI perfusion provides physiologic information about brain tissue biology, allowing the *in vivo* measurement of increased microvascularity and permeability to suggest tumor. ^{11, 12} There is growing evidence that MRI perfusion can improve the diagnosis and prognosis of patients with brain tumors over conventional imaging alone. ¹³⁻¹⁵ MRI perfusion correlates with microvessel density and vascular endothelial growth factor (VEGF) expression at histopathology and catheter based angiography. ^{16, 17} Two main methods of MR perfusion are currently being utilized to evaluate brain tumors – dynamic susceptibility contrast (DSC) perfusion imaging and dynamic contrast enhanced (DCE) perfusion imaging. DSC MRI perfusion is a T2* technique that relies on signal changes detected during the rapid bolus of contrast through brain tissues. Although small retrospective studies have suggested a role for MRI perfusion, ¹⁸⁻²¹ no prospective trial has been designed to distinguish between radiation injury and tumor progression.

DCE MRI perfusion is a T1 technique with superior spatial resolution that is beneficial in regions where hemorrhage or bone/air interfaces may otherwise limit DSC imaging. In addition, DCE provides potentially more robust absolute measurements of cerebral perfusion, flow and permeability – as opposed to the only relative measurements obtained by DSC. We propose studying the role of DCE MRI perfusion in distinguishing between focal radiation injury and tumor progression.

3.1.2 Rationale for the use of PET/CT

PET/CT is a commonly used technique in oncologic imaging that relies on combining the functional/physiologic information provided by PET imaging with the anatomic information provided by the concurrently acquired CT scan. As a proxy for cellular glucose uptake, FDG PET/CT can identify hypermetabolic lesions to suggest tumor. After the administration of a radiolabeled glucose analogue (F-18 FDG), relative metabolic activity in the brain can be imaged with tracer uptake directly correlated to the level of cellular glucose metabolism. In the brain, abnormal uptake can be determined by visual inspection and comparison to uptake in normal cortex or via quantification by measurement of standardized uptake values (SUV). No consensus SUV cut-off values for tumor detection have been established in the literature.²² Quantification of abnormal FDG uptake may also be performed by textural and topographc analysis using feature-based image analysis tools. Although retrospective reports²³⁻²⁹ suggest that PET imaging may play a role in distinguishing radionecrosis from tumor progression, this role has yet to be well defined in a prospective trial.

3.2 Preliminary Data

MRI perfusion and PET/CT are already routinely performed for patients with tumors with a history of brain radiation at MSKCC. In 2010, we performed 1,474 MRI perfusion scans and 212 PET/CT scans, for determining radiation injury as well as a variety of other reasons that include for staging, preoperative planning, preradiation therapy planning, and treatment follow up. The vast majority of the MRI perfusion scans were performed using

the DSC technique, with very few (<50) performed using the potentially more robust DCE technique.

In a preliminary retrospective analysis, we identified 12 consecutive patients over a one year period with indeterminate enhancing lesions after radiation therapy who underwent DSC MRI perfusion, FDG PET/CT, and subsequent surgical resection with pathologic diagnosis (Hatzoglou V, Ulaner G, Beal K, Zhigang Z, Young RJ; Abstract 9012072, Radiological Society of North America, Chicago, IL, December 2010). Both primary (n=3) and secondary (n=9) brain neoplasms were included. Seven patients received stereotactic radiosurgery (SRS, 18-21 Gy), 2 patients whole brain radiation (35-52.5 Gy) and 3 patients partial brain radiation therapy (59.4-60 Gy). From the PET/CT scans, standardized uptake values (SUV) of the lesion and background were measured by a board-certified nuclear medicine radiologist and ratios (SUV_{ratio}) calculated. From the DSC MRI perfusion images, maximal relative cerebral blood volume (rCBV_{max}) values were measured by a board-certified neuroradiologist. P-values were obtained using bootstrap or permutation tests, and receiver operating characteristic (ROC) analyses and areas under curve (AUC) were calculated.

We found that the SUV_{ratio} had the highest predictive value (AUC=0.943) for tumor progression, although this was not statistically better than any perfusion metric (AUC=0.757-0.829). After excluding two patients with hemorrhagic lesions, the AUC of the perfusion metrics improved slightly to 0.917-0.938.

This preliminary study found similar accuracy for PET/CT and MRI perfusion in distinguishing recurrent tumor from treatment necrosis. MRI perfusion performed better when patients with hemorrhagic lesions were excluded. These results have compelled us to develop a prospective trial, which will allow us to determine the optimal roles for PET/CT and MRI perfusion in the evaluation of patients with worsening enhancing lesions after treatment. We plan to perform DCE T1 perfusion instead of DSC T2* perfusion, as the DCE technique provides absolute measures of perfusion and permeability and is not limited by hemorrhage.

A systemic feature- or texture-based approach has been applied to PET scans in gynecological and head and neck cancers. This is similar to increasingly popular histogram analyses for other imaging data, 30 and has shown promise in treatment response analyses using multiparameter predictive models over single metrics such as simple SUV descriptive statistics. In a pilot study, correlation between feature-based predictive models and outcome improved by 14% in gynecological and 12% in head and neck cancers over SUV statistics.31

3.3 Exploratory use in patients treated with anti-angiogenic therapy

Bevacizumab is an anti-angiogenic therapy that is commonly used to treat patients with malignant gliomas (usually recurrent) as well as some systemic tumors (e.g., breast). In these cases, the use of contrast enhancement to determine response as performed in daily clinical practice and as defined by many clinical protocols, is less reliable.³² This is because bevacizumab may induce rapid decreases in contrast enhancement at imaging not accompanied by actual reductions in tumor. An alternative imaging marker to determine tumor progression in these patients is necessary.

Several studies have described decreased perfusion and decreased enhancement after anti-angiogenic therapy.³³⁻³⁵ This has been postulated to be due to normalization of the blood-brain barrier rather than decreased tumor burden. The exploratory endpoint concerns the growing use of anti-angiogenesis therapy (such as bevacizumab) in brain

tumor patients. Although direct effects on the vasculature may also affect perfusion, the precise effects involved remain poorly understood. The effects upon FDG uptake are similarly poorly understood, although the effects on glucose metabolism may be less dramatic than the effects on the vasculature. We believe that adding these patients to an exploratory endpoint will help us improve our understanding of the imaging effects of antiangiogenic therapy and develop better imaging tools to determine tumor progression.

Exploratory Endpoint:

1. To assess the utility of PET and MRI perfusion studies in predicting tumor progression in patients with malignant gliomas receiving anti-angiogenic therapy (such as bevacizumab). Due to direct drug effects upon the vasculature, these tumors often show little or no enhancement despite clinical worsening and increasing non-enhancing abnormalities. Therefore, we often cannot rely on changes in size of the contrast enhancing mass lesion as usual. The role of advanced imaging in determining progression in lesions that do not show increased enhancement has not been defined. In an exploratory fashion, we will enroll patients with malignant gliomas receiving anti-angiogenic therapy with suspected progression and increased nonenhancing lesions. Analysis will be similar to that for patients under the Primary Endpoint.

3.3.1 Exploratory use of advanced diffusion imaging

Restriction spectrum imaging (RSI) is an advanced diffusion technique that models diffusion signal by incorporating tissue parameters such as the size, shape and orientation fo water diffusion. RSI offers the ability to separate the diffusion components according to the different tissue types, potentially improving tumor margin conspicuity. By maximizing the diffusion signal from within tumor cells while minimizing diffusion signal from edema, RSI may be useful in evaluating tumor progression and in particular patients treated with anti-angiogenic agents such as bevacizumab⁵⁶.

3.4 Benefits

The proposed study will make a significant contribution to our understanding of the optimal imaging evaluation of neoplasms treated with brain radiation therapy. Determining the presence of tumor progression can directly impact patient therapy. If the data indicates that MRI perfusion and/or PET/CT (alone or in combination) can accurately predict the presence of radiation injury or tumor progression, then potential treatment options could be pursued at an earlier point in the patient's course and thereby potentially improve patient survival. This information will likely also be very useful for neurosurgical planning to maximize the timing and resection of lesions that require surgical management. The nonsurgical treatments for these two entities are different, as tumors may benefit from additional chemotherapy and radiation therapy, whereas radiation injury will be worsened by additional radiation therapy and likely not helped by chemotherapy.

In addition, if the results indicate that MRI perfusion is comparable to or superior to PET/CT, several patient and systemic advantages may emerge. First, nearly all patients with a history of radiation therapy to the brain undergo MRI scans for surveillance after treatment, whereas PET/CT is reserved as a problem-solving tool. Therefore, MRI perfusion is more convenient for patients, as it may be obtained at the time of their routine MRI scan, and does not require a separate appointment. MRI perfusion requires 5 minutes to acquire, but does not require any additional intravenous contrast. The 3D workstation charge associated with MRI perfusion is much less than the charges associated with PET/CT. In addition, MRI has no radiation risk, in contrast to the very small but present risk with PET/CT.

By designing this as a prospective study, we will minimize the potential biases and variability of a retrospective analysis. Both MRI perfusion and FDG PET/CT scans are part of the standard of care for patients with indeterminate lesions after treatment. The purpose of this study is to prospectively enroll these patients in order to standardize the scanning intervals and formalize the imaging, evaluation and follow up of these patients. What we learn may improve our understanding of radiation injury and thus benefit society and future brain tumor patients.

This research project will help develop the career of the P.I., who has published several papers in peer-reviewed journals about the advanced MRI technique in evaluating malignant gliomas. MRI perfusion is regarded as a very important tool in the diagnosis, prognosis and management of brain tumors and treatment complications. Although the older T2* technique has been used for >10 years, there is still avid interest and research into the optimal imaging parameters, reconstruction algorithms, processing techniques and clinical relevance. This is particularly true for the newer T1 perfusion technique proposed in this protocol. The P.I. has given invited talks at national meetings and built a reputation as an innovative clinical investigator with abundant experience in advanced MRI techniques. The P.I. anticipates that the data collected from this project will be an essential part of a subsequent R21 quick trial or similar grant to the NIH.

4.0 OVERVIEW OF STUDY DESIGN/INTERVENTION

4.1 Design

Accrual: In 2011, a total of 825 patients were treated at MSKCC for a brain tumor with surgery, radiation therapy (n=286+) and/or chemotherapy (Caisis database, accessed 3/1/2012). In 2010 and 2011, a total of 86 patients had suspected radiation injury and underwent surgical resection of their lesions (outcomes consisted of "recurrent/residual tumor with treatment effect" and "non-cancer" diagnoses at histopathology). The ratio of nonsurgical vs. surgical treatment for patients with suspected radiation necrosis at MSKCC is estimated at 2-3:1, based on our recent study³⁶ on suspected pseudoprogression (early radiation injury in high grade glioma patients) and observed patterns from imaging studies and multidisciplinary tumor board discussions. Extrapolating from the 86 patients with suspected radiation injury and subsequent histopathology, we estimate that approximately 258-344 patients over 2 years undergoing brain tumor treatment at MSKCC may have a concern of radiation injury. Based on accrual rates for similar protocols at MSKCC, and our accrual rate thus far (75 patients over 2 years), the estimated accrual for this study is 2-4 patients per month. We plan to enroll approximately 35 patients per year, for a total of 150 patients over a 4 year period. We will continue to follow up until death or a year after the patient's last MRI if he/she is lost to follow up.

The study will prospectively enroll patients who have increasing size and/or enhancement of brain lesion(s) after brain radiation therapy for a neoplasm (either primary or metastatic), where it is unclear if a lesion represents radiation injury or progressive tumor. The procedures and the minimal risks of MRI perfusion and PET/CT are the same regardless of the situation (tumor type or radiation plan) in which they are applied. We apply identical processing procedures to analyze the data regardless of the original tumor type or radiation therapy regimen, and when applicable apply identical imaging metric thresholds. Radiation injury may occur after stereotactic radiosurgery, partial brain

radiation, or less commonly after whole brain radiation therapy. The most important factors for developing radiation injury are radiation dose, schedule and fractionation. We will for the purposes of this protocol assume that the subject population is homogeneous (given a common radiation injury mechanism and imaging manifestations) and recruit to a single subject cohort.

In addition to studying all enrolled patients as a single cohort, we will at the end of the study examine specific subcohorts as described in the following specific clinical scenarios. This will help us to determine if there are any differences in our techniques and measurements between groups.

Specific clinical scenarios when PET/CT and MRI perfusion may be clinically necessary to examine indeterminate lesions:

- 1) Gliomas after radiation therapy with increased or new enhancing lesions
- 2) Gliomas after radiation therapy in patients receiving bevacizumab or other antiangiogenic chemotherapy with increased or new enhancing and/or non-enhancing lesions
- 3) Metastases after radiation therapy with increased or new enhancing lesions
- 4) Metastases after radiation therapy who may be receiving bevacizumab or other antiangiogenic chemotherapy for systemic or brain disease

This is a nonrandomized study in which each patient will receive the standard clinical care (in the form of surgery, radiation treatment and/or chemotherapy) as per the treating physician(s). Upon enrollment, the patients will undergo both MRI perfusion and PET/CT imaging, preferably on the same day to maximize patient convenience and reduce potential changes between scans, but at most within 12 weeks of one another. The two scans will be performed within 12 weeks after the indeterminate lesion is initially identified (unless the screening scan is a DCE MRI perfusion, in which case it will serve as the protocol MRI intervention as well). The neuroradiologist reading the MRI and nuclear medicine physician reading the PET/CT will be blinded to each other's interpretation and the patient's treatment protocol. Based on both the standard of practice at our institution and existing guidelines in the literature, the nuclear medicine physician and neuroradiologist will independently predict the most likely outcome for each lesion: radiation injury vs. tumor progression. Only the results of the first MRI perfusion and FDG PET/CT will be used for data analysis (some patients may require repeat scans as part of their standard of care, as per their treating physician).

Patient outcome will be determined by a neuro-oncologist using standard histopathologic or clinical and imaging follow-up criteria (excluding any subsequent MRI perfusion or FDG PET/CT data). Unless the patient requires surgery as part of the standard of care for their brain tumor, the diagnosis will be established by follow up. Patients will remain on study until the completion of either the MRI perfusion or PET/CT that are within 12 weeks of each other. After one of these scans, the patient will have no active interventions and will be off study. Follow up will occur approximately every 2-3 months as per the treating physician and the standard of care (most gliomas are followed every 2 months, most metastases every 3 months). Follow up is expected to take 6 months or less in most patients, although some patients with slowly growing or otherwise confusing lesions may require longer follow up.

4.2 Intervention

The MRI perfusion and PET/CT scans will be obtained within 12 weeks of each other. These scans are part of the standard of care for patients with brain tumors and uncertain tumor response or progression after treatment. Although every effort will be made to perform both MRI perfusion and PET/CT on the same day or during the same week, some patients may experience longer intervals between scans due to scheduling conflicts. The disease in question (radiation injury vs. tumor progression) may change slightly during this interval (e.g., the lesion may grow or shrink slightly), but no large changes are expected between the two scans. The patients may continue existing treatments in the interval between scans (e.g., steroids, chemotherapy), but the two scans must be performed before any change or new treatment occurs. Fusion images of MRI and PET/CT will not be reviewed by the neuroradiologist interpreting the MRI perfusion nor the nuclear medicine radiologist interpreting the PET/CT.

4.2.1 MRI perfusion:

Dynamic contrast enhanced (DCE) T1 perfusion will be performed per standard of care using (1) an axial 3D spoiled gradient-recalled acquisition in the steady state (SPGR) sequence with these or similar parameters: TR/TE=8.3/1.5; flip angle 25°; matrix 256x128x128; slice thickness 5 mm; field-of-view 24 cm; acquisition time 10 seconds per volume of 12-18 slices; acquired 40 times, once before and 39 times immediately after intravenous bolus administration of a single dose of contrast material; - or - (2) an axial 3D differential subsampling with Cartesian ordering (DISCO) sequence with these or similar parameters: TR/TE=4.5/1.8; matrix 288x160; slice thickness 4 mm; field-ofview 24 cm; acquisition time 10 seconds per volume of 35-40 slices; acquired 40 times, once before and 39 times immediately after intravenous bolus administration of a single dose of contrast material. Both sequences will require approximately 5 minutes of scanning time. SPGR MRI perfusion does not allow whole brain coverage due the dynamic nature of the contrast injection. If multiple lesions exist, then the lesion(s) of clinical concern (e.g., the lesion(s) that is growing) or the largest lesion(s) will be interrogated and as many other lesions as possible will be included in the perfusion volume. Although patients commonly receive treatment for multiple lesions, in our experience most (>90%) patients only have growth of one lesion whereas the other lesions remain stable. Only existing previously irradiated lesions at the time of enrollment will be considered target lesions for this study. The DISCO sequence is the updated, FDA approved sequence from GE Healthcare that is capable of whole brain coverage. DISCO has been adopted as the standard of care for MRI perfusion, where available on selected MRI scanners. Patients will receive DISCO perfusion if it is available. or the standard SPGR perfusion.

The data will be transferred to an off-line workstation running Windows platform for analysis using commercially available or research perfusion software packages, such as: NordicICE by NordicNeuroLab, which is a commercially available, FDA approved product. The software package performs pharmacokinetic modeling to analyze DCE T1 perfusion data.

The methods of analysis will include: region-of-interest (ROI) measurements of the lesion and normal brain will be performed. ROIs will be placed in the lesion while avoiding areas of hemorrhage, calcification, and cystic/necrotic change. This is the standard way of measuring lesions in clinical practice. Multiple small ROIs will be placed, and the maximum recorded, a technique that has been described as providing the best reproducibility.^{37, 38} Recorded metrics will include: plasma volume (Vp) and volume transfer coefficient between plasma and extravascular extracellular space (K^{trans}). We may also use volume of interest (VOI) measurements of the entire lesion.

Additional postprocessing: Feature-based analyses will be performed on an investigational basis. These are not routinely performed as part of the standard of care, and therefore the results will be only for research and not included in the MRI report. The DCE maps will be processed using in-house routines developed in C++ and Matlab for extracting image-based textures and Gabor edge features to characterize each lesion in terms of topological and textural factors. In-house developed machine learning techniques may be applied to automatically find correlations between image features and lesion outcomes.

4.2.2. PET/CT: Patients will fast except for water ± medications (as per their clinical physician) for at least 6 hrs prior to this study. The patient is seated comfortably in the injection room and venous access is established. The patency of the venous access is checked with normal saline prior to the administration of the FDG.

Blood glucose is checked by finger stick. If blood glucose is >60 and <200mg/dL the study continues as planned. If the blood sugar is between 200 and 300mg/dL, then a standard insulin administration protocol is used to bring the blood glucose below 200. If blood glucose is > 300mg/dL, the study is rescheduled. If the blood glucose is <60, juice is given orally and the study is rescheduled.

10 mCi of Fluorine-18 fluorodeoxyglucose (FDG) is injected IV. The patient remains seated quietly in the injection room for 60 minutes. The patient is then positioned on a GE Discovery STE PET/CT. A scout view of the head is acquired at 30 mA, 120 kVp. Once the scanning field is determined from the scout, a spiral CT is acquired using a full helical acquisition at 1 sec/rotation, 30 mA, 140 kV, 5.0 mm slice thickness, 4.5 mm interval. Immediately upon completion of the CT, acquisition of a 10-minute 3D brain PET scan is performed. CT and PET data are re-reconstructed using a 30 cm FOV. CT, PET, and hybrid images are evaluated in transaxial, coronal, and sagittal planes. The standardized uptake value (SUV) of the lesion (SUV_{lesion}), normal brain (SUV_{normal}) and SUV_{ratio} (SUV_{lesion}/SUV_{normal}) will be calculated using standard ROI tools. PET/CT allows whole brain coverage. Measurements of each lesion will be performed and each lesion evaluated independently for radiation injury vs. tumor progression.

Additional postprocessing: Feature-based analyses will be performed on an investigational basis. These are not routinely performed as part of the standard of care, and therefore the results will be only for research and not included in the PET report (as compared to SUV, which are standard of care and reported to the clinician). The PET scans will be processed using CERR (Computational Environment for Radiotherapy Research) and/or in-house routines developed in C++ and Matlab for extracting image-based textures and Gabor edge features to characterize each lesion in terms of topological and textural factors. In-house developed machine learning techniques may be applied to automatically find correlations between image features and lesion outcomes. We may also investigate novel analysis methods in addition to SUV by using other correction factors for normal tissue selection and ratio calculations.

4.2.3 Advanced diffusion imaging (Optional): RSI acquisition will require approximately 4-5 min, similar to the time required for the standard of care DTI acquisition. The only thing noticeable by the patient will be the extra scan time required to acquire DSI. The patient will be requested to remain motionless during this scan.

RSI will be acquired using a single-shot gradient spin-echo echo-planar sequence with these or similar parameters: 6-15 directions, TR=96 msec, TE=17 msec, matrix 128x128, slice thickness 3 mm, b-values 0-4000 s/mm2. Total of 40-45 direct axial slices with no interslice gap will be obtained to cover the entire brain. The sequence will require 4-5 min.

Post-processing will be performed using software that will be provided to MSKCC by GE Global Research. The acquired data will be analyzed on an offline workstation, after the RSI data have been acquired and after the patient has left the MRI suite.

At the discretion of PI the RSI sequence may be repeated at SOC FDG or other radiotracer imaging carried out while the patient is still on study, if deemed clinically necessary.

5.0 CRITERIA FOR SUBJECT ELIGIBILITY.

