To further consider the variation among radiation doses, fractionations and schedules (which may be employed as per the standard of care for the specific tumor type in each patient), a more complicated ANCOVA (analysis of variance with covariates) will be used with the above parameters specified as covariates. If the numbers are small, we will summarize the results descriptively and suggest future research directions. We estimate that 15-25% (21-35 patients of the total) will undergo repeat surgical resection or biopsy to determine the diagnosis. A separate subset analysis will examine for potential differences between lesions diagnosed by pathology vs. lesions diagnosed by clinical and radiological follow up.

Most of the time, the two imaging methods (i.e., MRI perfusion and PET/CT) are expected to yield concordant results (>80%). Therefore, it is meaningful to compare the predictive power of various MRI perfusion measurements and PET/CT measurements. Due to the multiple comparisons needed, an FDR approach will be employed to control for the family-wise error rate. We may further construct a decision rule by combining results from both techniques in the hope of identifying an even more powerful predictive tool, although its feasibility would depend on the exact number of discordant cases and the individual

predictive power (if both MRI perfusion and PET/CT have sufficient predictive power and there are too few discordant cases then the combination may not show significant improvement).

As mentioned above, an interim analysis will be performed after 1 year or accrual of 48 (1/2 of expected total) subjects. Statistical tools may be adjusted at that time point if necessary to account for higher or lower than expected accruals within subgroups. For example, if many more than expected patients have uncertain outcomes or death before diagnosis (without autopsy), then we will may increase the target accrual to compensate.

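### SPGR and DISCO perfusion values would be pooled with no sequence term or stratum, so any shift between sequences would bias the MRI AUC but not the PET AUC it is compared with

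*Combined protocol and SAP*

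**What the plan says.** Section 4.2.1 describes two DCE acquisitions. SPGR is listed with "TR/TE=8.3/1.5; flip angle 25°; matrix 256x128x128; slice thickness 5 mm", covering 12-18 slices. DISCO is listed with "TR/TE=4.5/1.8; matrix 288x160; slice thickness 4 mm", covering 35-40 slices and with no flip angle given. Which one a patient gets depends on the scanner: "Patients will receive DISCO perfusion if it is available"; otherwise SPGR is used.

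The MRI metrics are Vp and Ktrans (sections 4.2.1 and 7.1). On how they are read: "Multiple small ROIs will be placed, and the maximum recorded". Whole-lesion volumes of interest may also be used. Normal brain is measured too, but no rule for normalizing the MRI values to it is stated. For PET, section 4.2.2 names one scanner model and one acquisition, and a lesion-to-normal SUV ratio is among the metrics.

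Section 11.1 compares the modalities by the difference in AUC, with bootstrap intervals. Its adjustment model is introduced by "To further consider the variation among radiation doses, fractionations and schedules" and then: "a more complicated ANCOVA (analysis of variance with covariates) will be used with the above parameters specified as covariates". Those parameters are the radiation ones. Sequence and scanner appear nowhere in the t-tests, the ROC analysis, the ANCOVA, the subcohorts of 11.2 or the GEE of 11.3.

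**The concern.** The primary goal in section 2.0 is a direct comparison of PET/CT with MRI perfusion. If the same tissue gives systematically different Vp or Ktrans under the two sequences, a pooled ROC curve ranks a DISCO patient against an SPGR patient partly on the machine used. That error enters the MRI curve only, so the head-to-head comparison is exposed on one side.

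There are reasons to allow for a shift, although none proves one. The listed timing, matrix and slice thickness differ, and a maximum over small regions is in general sensitive to voxel size and noise. A mix of sequences is also plausible: section 4.2.1 says DISCO is available on selected scanners only, and section 4.1 reports 75 patients already accrued.

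**Working it through.** **1. The plan's own figure.** Section 11.1 gives no power for an AUC or an AUC difference. It gives type II errors of about 10% and 1% for a one-sided 5% two-sample t-test with 150 patients at effect sizes 0.5 and 0.7. Splitting 150 in the anticipated 90:42 ratio (102.3:47.7) gives power 0.886 and 0.991, so these figures reproduce.

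**2. Nominal voxel volumes** (24 cm field of view, listed matrix and slice thickness):
- SPGR: 240/256 × 240/128 × 5 = 8.79 mm³
- DISCO: 240/288 × 240/160 × 4 = 5.0 mm³, which is 43% smaller

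This shows that the acquisitions differ. It cannot be converted into a shift in Vp or Ktrans.

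**3. Pooled AUC, sequence unrelated to outcome.** Assumptions: normal values with unit SD, tumor and injury means d apart, DISCO adding a constant s (in SD), half the patients on each sequence. With F(x) = Φ(x/√2),

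pooled AUC = 0.5 F(d) + 0.25 F(d+s) + 0.25 F(d−s).

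A true AUC of 0.80 means d = √2 × Φ⁻¹(0.80) = 1.19.

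| s | F(d+s) | F(d−s) | Pooled AUC | Loss |
|---|---|---|---|---|
| 0.5 | 0.884 | 0.687 | 0.793 | 0.007 |
| 1.0 | 0.939 | 0.554 | 0.773 | 0.027 |
| 1.5 | 0.971 | 0.413 | 0.746 | 0.054 |

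For scale, the Hanley-McNeil standard error of an AUC of 0.80 with 90 and 42 patients is about 0.038. The losses are therefore about 0.2, 0.7 and 1.4 standard errors.

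**4. Sequence related to outcome.** With DISCO shares p1 in tumor and p0 in injury,

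pooled AUC = [p1p0 + (1−p1)(1−p0)] F(d) + p1(1−p0) F(d+s) + (1−p1)p0 F(d−s).

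Take d = 0.7, where the true AUC is 0.690:
- 60% DISCO in tumor and 40% in injury: the AUC changes by +0.019 (s = 0.5) or +0.027 (s = 1).
- 40% in tumor and 60% in injury: it changes by −0.030 or −0.067.

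Chance imbalance is enough to matter. The SD of p1−p0 is √(0.25/90 + 0.25/42) = 9.3 percentage points. The imbalance at which the AUC bias is zero is only 4.3 points (s = 0.5) or 8.4 points (s = 1). In simulation with sequence independent of outcome, the shifted pooled AUC still exceeded the unshifted one in 34% (s = 0.5) and 21% (s = 1) of trials.

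**5. Effect on the MRI-PET comparison.** Simulation: 90 tumor and 42 injury patients, one lesion each, 50% DISCO, truly equal AUCs, MRI-PET correlation 0.5 or 0.8, paired DeLong test. The table gives the chance of declaring PET better (nominal 2.5%).

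| True AUC | s = 0.5 | s = 1 | s = 1.5 |
|---|---|---|---|
| 0.690 | 3% | 6-7% | 10-13% |
| 0.829 | 4% | 10-13% | 22-32% |

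The value 0.829 is the top of the preliminary perfusion range in section 3.2, which was obtained with DSC in 12 patients.

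**6. Effect on the t-test.** At d = 0.5 a shift inflates the SD to √(1 + 0.25s²). Power falls from 0.886 to 0.869 (s = 0.5) and 0.818 (s = 1).

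**7. Price of the remedy.** A within-sequence AUC returns the unshifted value. With no shift at all and a true AUC of 0.80, its simulated SD is 0.0407, against 0.0401 for the pooled AUC (0.0407/0.0401 = 1.015).

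**The case against.** The strongest reply is that no shift has been shown. Sections 3.1.2 and 3.2 choose DCE partly because it yields absolute rather than relative measurements, and section 4.2.1 puts the data through pharmacokinetic modeling. If that works as hoped, the sequences may agree closely. The voxel figures are nominal (the protocol allows similar parameters) and region size is not stated. At 0.5 SD the loss is well inside sampling error. All of this stands and keeps the point modest. It does not show that the sequences are equivalent, and no section says that they are.

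A reader might go further in three ways that the documents do not support.
- **That the plan commits to the same cut-offs for SPGR and DISCO.** The sentence in section 4.1 reads "regardless of the original tumor type or radiation therapy regimen, and when applicable apply identical imaging metric thresholds". It concerns tumor type and radiation regimen, is conditional, and does not mention sequence. An AUC uses no cut-off in any case. Pooling is inferred from the absence of a sequence term.
- **That any shift must lower the MRI AUC and favor PET.** This holds only in expectation, and only when sequence is unrelated to outcome (step 4).
- **That every MRI result is affected.** Section 4.1 also has each reader predict the outcome. A numerical shift does not carry mechanically into that judgment, so the exposure is in the quantitative metrics.

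**Conclusion.** The omission is real: two sequences are assigned by availability, and no planned analysis separates them. The consequence is conditional. If SPGR and DISCO values are shifted, the pooled MRI AUC is biased while the PET AUC is untouched. At a 50:50 mix and a true AUC of 0.80 the expected loss is 0.007 at 0.5 SD, 0.027 at 1 SD and 0.054 at 1.5 SD. That is negligible at the low end and enough to distort the modality comparison from about 1 SD. The shift, the mix and the normal model are assumptions, since the documents give none of them. This is a cheap improvement to the analysis and does not call the design into question.

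**What to change.** In section 11.1:
1. Record the sequence (SPGR or DISCO) for each protocol scan. It is not among the items listed in section 7.1, so the plan should say so.
2. For the MRI-PET comparison, compute the MRI AUC from tumor-injury pairs scanned with the same sequence, combine across the two sequences, and bootstrap within sequence. Section 4.1 uses only the first perfusion scan, so sequence is fixed within a patient and patients can be the resampling unit.
3. Report the pooled AUC as a sensitivity analysis.
4. Add sequence as a covariate in the MRI mean comparison and ANCOVA. This protects the test of means but leaves the AUC comparison uncorrected, so it cannot replace item 2.

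The cost is a few sentences and one variable that can be taken from the acquisition. If there is no shift, the loss of precision is about 1.5% in the SD of the AUC. The within-sequence AUC removes a common shift in either direction. It does not address a real difference in discrimination between sequences, which separate AUCs by sequence would show descriptively.
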